10.2 Handling of Multiplicity

There will be no hypothesis testing for the primary and secondary efficacy endpoints. Therefore, there will be no adjustment for multiple endpoints.

10.3 Primary Efficacy Analysis

The primary efficacy endpoint is the percentage of subjects who achieve SVR₁₂ (HCV RNA < LLOQ 12 weeks after the last actual dose of study drug) based on the overall ITT population. The number and percentage of subjects achieving SVR₁₂ will be calculated along with a two-sided 95% CI using the normal approximation to the binomial distribution, unless the number of SVR₁₂ non-responders is less than 5, where the Wilson's score method¹ will be used to calculate the CI instead.

A summary of the reasons for SVR₁₂ non-response (e.g., on-treatment virologic failure, relapse, other) will be provided. A listing of subjects who do not achieve SVR₁₂ by reason for non-response will also be provided.

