8.1.2.1 Primary Efficacy Endpoints

The primary efficacy endpoint is the percentage of subjects who achieve SVR₁₂ (HCV RNA < LLOQ 12 weeks after the last actual dose of study drug) across all genotypes (GT1 – 6 subjects) will be analyzed on combined treatment groups. The primary endpoint will be analyzed based on intention to treat (ITT) population. The number and percentage of subjects achieving SVR₁₂ will be summarized with a two-sided 95% confidence interval using the normal approximation to the binomial distribution, unless the number of SVR₁₂ non-responders is less than 5, in which case the Wilson's score method will be used for the confidence interval instead.

A summary of reason for SVR₁₂ non-response (e.g., OTVF, relapse, other) will be provided.

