4.3 Sample Size

It is anticipated that a total of approximately 100 HCV infected treatment naïve GT1 – 6 subjects will be enrolled in this study. No formal hypothesis is being tested. If

the observed SVR₁₂ rate in this study is 97% among 100 HCV GT1 – 6 treatment naive subjects, then the half-width of 2-sided 95% normal approximation to the binomial distribution confidence interval will be 3.3% (EAST 6.4).

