6.3 Missing Data Imputation

Missing Data Imputation for SVR

HCV RNA values will be selected for analysis based on the analysis windows defined in Section 6.2.

For analyses of SVR, subjects missing visit values will have backward imputation applied, if possible. For backward imputation, if the nearest HCV RNA value after the SVR window is unquantifiable or undetectable, then it will be used to impute the HCV RNA value in the SVR window. If a subject is missing an HCV RNA value within the appropriate SVR window after performing backward imputation, then this value will be imputed with an HCV RNA value from a local laboratory if present; otherwise, the HCV RNA value will be missing. Subjects with missing HCV RNA data in the analysis window, after imputations, will be imputed as a failure.

Regardless of the imputation method described above, if a subject starts another treatment for HCV, then all HCV RNA values for this subject measured on or after the start date of the new HCV treatment will be excluded from analyses. The subject will be considered a failure for summaries of viral response at all time points after the start of the new HCV treatment.

Missing Data Imputation for Virologic Failure

If HCV RNA values from the central laboratory are missing but a local laboratory value is present in the appropriate time period, then the local laboratory value will be used to assess post-treatment relapse and on-treatment virologic failure.

Missing Data Imputation for PRO Questionnaires

If a respondent answers at least 50% of the items in a multi-item scale of the SF-36v2, the missing items will be imputed with the average score of the answered items in the same scale. In cases where the respondent did not answer at least 50% of the items, the score

for that domain will be considered missing. The Mental and Physical Component Summary measures will not be computed if any domain is missing. For TSQM, if a respondent answers at least 2 items in the 3 item scales of Side Effects or Effectiveness, the missing items will be imputed with the average score of the answered items in the same scale. For EQ-5D-3L, health state index and VAS scores no imputation will be performed for missing items.

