10.5 Sensitivity Analyses for SVR

The two-sided 95% confidence interval using Wilson's score method will also be calculated as a sensitivity analysis for the primary endpoint of SVR₁₂ based on ITT population.

As sensitivity analyses, the number and percentage of subjects in the mITT-VF population achieving SVR₁₂ will be summarized by genotype and overall, along with a two-sided 95% confidence interval using the normal approximation to the binomial distribution and a two-sided 95% confidence interval using the Wilson's score method. Listings of subjects excluded from mITT-VF population will be provided, as applicable.

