12.0 Summary of Changes

12.1 Summary of Changes Between the Latest Version of the Protocol and SAP

- Remove demographic and baseline characteristic analyses, subgroup analysis related to HCV/HIV Co-infection subjects because no HCV/HIV Co-infection subjects enrolled

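### The primary SVR12 interval changes method at 5 non-responders, and at that point one more non-responder raises both confidence limits

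*SAP*

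**What the plan says.** SAP 10.3 gives the number and percentage of ITT subjects with SVR12 and a two-sided 95% interval "using the normal approximation to the binomial distribution, unless the number of SVR₁₂ non-responders is less than 5"; below that count, "Wilson's score method¹ will be used to calculate the CI instead". Protocol 8.1.2.1 sets the same switch: "non-responders is less than 5, in which case the Wilson's score method will be used for the confidence interval instead". So 0 to 4 non-responders lead to Wilson, and 5 or more to the normal approximation.

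Four other places bear on this:

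- SAP 4.3 plans for about 100 subjects, tests no hypothesis, and states precision at an observed 97% as "half-width of 2-sided 95% normal approximation to the binomial distribution confidence interval will be 3.3" per cent.
- SAP 10.5 adds that an interval by "Wilson's score method will also be calculated as a sensitivity analysis for the primary endpoint", on the ITT population. Wilson is therefore reported at any count.
- SAP 6.3 counts missing results as non-response: "Subjects with missing HCV RNA data in the analysis window, after imputations, will be imputed as a failure".
- SAP 10.4, 10.6 and 10.7 use Wilson alone for the secondary endpoints, the subgroups and the additional endpoints.

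**The concern.** An interval for a proportion should move down when a success becomes a failure. Here the method changes between 4 and 5 non-responders, and near a proportion of 1 the two methods differ a good deal. Wilson pulls its centre towards one half. The normal approximation stays centred on the estimate. Moving from the first to the second at the moment the estimate drops can push both limits the wrong way.

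The fifth non-responder need not be a virologic failure. Under SAP 6.3 a subject with no usable HCV RNA value in the window also counts, so one missed visit could change the method and apparently improve the interval.

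What is at stake is the coherence of the interval labelled primary and of the planning precision. No decision threshold is involved.

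**Working it through.** **Inputs.** Two-sided 95% intervals (protocol 8.1), so z = 1.960. N = 100 (SAP 4.3), with 90 to 110 also checked because enrolment is approximate. Planning rate 97% (SAP 4.3). Treatment-naïve rate 1604/1640 = 97.8% (protocol Table 2).

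**Formulas.** With p the observed proportion:

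- Normal approximation: p ± z·√(p(1−p)/N).
- Wilson: [p + z²/(2N) ± z·√(p(1−p)/N + z²/(4N²))] / (1 + z²/N).

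**The plan's own figure.** At 97/100 the normal half-width is 1.960 × √(0.97 × 0.03/100) = 3.34 points, which reproduces the stated 3.3%. That interval is 93.66% to 100.34%, so it runs past 100%. With 3 non-responders SAP 10.3 calls for Wilson, which gives 91.55% to 98.97%, a half-width of 3.71 points.

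**The switch at N=100.**

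- 4 non-responders, Wilson: centre (0.96 + 0.01921)/1.03841 = 0.9430; half-width 1.960 × √(0.000384 + 0.000096)/1.03841 = 0.0414; interval 90.16% to 98.43%.
- 5 non-responders, normal approximation: half-width 1.960 × √(0.95 × 0.05/100) = 0.0427; interval 90.73% to 99.27%.

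| Non-responders | Planned primary interval | Wilson |
|---|---|---|
| 3 | 91.55–98.97 (Wilson) | 91.55–98.97 |
| 4 | 90.16–98.43 (Wilson) | 90.16–98.43 |
| 5 | 90.73–99.27 (normal) | 88.82–97.85 |
| 6 | 89.35–98.65 (normal) | 87.52–97.22 |

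From 4 to 5 the lower limit rises by 0.57 and the upper by 0.84 points. The upper limit at 6 (98.65) is still above the one at 4 (98.43). With Wilson throughout, both limits fall from 4 to 5, by 1.34 and 0.59 points.

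**Other sample sizes.** At N = 90, 95, 105 and 110 the lower limit rises by 0.54 to 0.59 points and the upper by 0.77 to 0.92. Both limits rise at every N from 34 to 1000.

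**Chance of reaching the normal branch.** The binomial probability of 5 or more non-responders among 100 is 7% at a true rate of 97.8% and 18% at 97%. At 96%, an assumed less favourable rate that the documents do not use for planning, it is 37%.

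**Coverage.** Exact binomial coverage at N=100, over true rates from 94% to 98% in steps of 0.0001:

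| Rule | Minimum | Maximum | Average |
|---|---|---|---|
| As planned | 96.7% | 99.9% | 98.8% |
| Wilson throughout | 92.7% | 97.8% | 95.6% |

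Over the wider range of 88% to 99%, the planned rule falls to a minimum of 90.9%, near a true rate of 89.3%, well below what is expected here.

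**The case against.** The rule is deliberate and prespecified. The rationale given with Amendment 1 is that the normal approximation covers poorly at high SVR12 rates, and protocol and SAP agree on the remedy. In the expected range it never covers below 95%, whereas Wilson drops to 92.7% at its worst and lies below 95% on about 30% of the grid. The trial will produce one count, so the reversal shows only when hypothetical results are compared. With 5 or more non-responders a reader sees both intervals anyway. Changing a prespecified primary method late in an open-label study invites a post-hoc challenge. The 3.3% in SAP 4.3 is correct as labelled.

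Much of this stands, and it is why the point is minor. Wilson's lower minimum coverage is a real trade-off. It does not rescue the switch, however: the planned rule buys its minimum by over-covering at 98.8% on average, while Wilson averages close to the nominal 95%. The Amendment 1 reasoning also points to Wilson at 5 non-responders, since 95% is still a high rate. A late change could not favour the product, because Wilson is identical for 0 to 4 non-responders and gives lower limits at both ends at 5 and 6. Counting missing data as failure is not itself a fault of the switch; it only shows how the count may reach 5. The SAP 4.3 figure contains no arithmetic error, but it does not describe the interval that would be reported in that case.

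**Conclusion.** The concern holds, as a minor one. At N=100 the step from 4 to 5 non-responders raises the primary limits by 0.57 and 0.84 points while the estimate falls by 1 point, and the pattern is the same at any final N near 100. The branch is reached with probability 18% if the true rate is the planned 97%, and 7% if it is 97.8%. The stated planning half-width is 0.4 points smaller than that of the interval SAP 10.3 would give at 97/100.

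This is a defect of consistency and presentation. There is no under-coverage at true rates of 94% to 98%, and no test depends on the interval. The practical question is which of two reported intervals is called primary. The figures assume Wilson without continuity correction; with correction on both methods at N=100 both limits still rise (89.49–98.71% to 90.23–99.77%).

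**What to change.** - **SAP 10.3:** name the two-sided 95% Wilson score interval as the primary SVR12 interval at every count.
- **SAP 10.5:** replace the ITT Wilson line with the normal-approximation ITT interval, labelled supplementary.
- **SAP 4.3:** restate the precision at 97/100 as Wilson 91.5% to 99.0%.
- **SAP 12.1:** record the departure from protocol 8.1.2.1 under "Summary of Changes Between the Latest Version of the Protocol and SAP". Because the study is open-label, date the entry before any data lock, including the optional interim lock in SAP 4.4. Align protocol 8.1.2.1 if there is a further amendment.

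These are text edits. No new programming is needed, since Wilson is already planned for ITT SVR12. There are three costs. Protocol and SAP differ openly on the primary interval until an amendment. Minimum coverage in the expected range falls from 96.7% to 92.7%. With 5 non-responders the primary lower limit is less favourable by 90.73 − 88.82 = 1.9 points at N=100, or 2.1 points at N=90.

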10.4 Secondary Efficacy Analyses

The secondary efficacy endpoints are:

- The percentage of subjects with HCV on-treatment virologic failure (defined as confirmed increase of > 1 log₁₀ IU/mL above nadir during treatment, confirmed HCV RNA ≥ 100 IU/mL after HCV RNA < LLOQ during

treatment, or HCV RNA \geq LLOQ at the end of treatment with at least 6 weeks of treatment), and

- The percentage of subjects with Relapse₁₂ (defined as confirmed HCV RNA \geq LLOQ between end of treatment and 12 weeks after the last dose of study drug among subjects who completed treatment as planned with HCV RNA $<$ LLOQ at the end of treatment; excluding subjects who have been shown to be reinfected).

For the analysis of post-treatment HCV virologic relapse, completion of treatment is defined as any subject with study drug duration of 52 days or greater and 77 days or greater for subjects allocated to treatment durations of 8 weeks and 12 weeks, respectively.

For on-treatment virologic failure and post-treatment relapse, the number and percentage of subjects will be summarized along with a two-sided 95% CI using Wilson's score method.

10.5 Sensitivity Analyses for SVR

The two-sided 95% confidence interval using Wilson's score method will also be calculated as a sensitivity analysis for the primary endpoint of SVR₁₂ based on ITT population.

As sensitivity analyses, the number and percentage of subjects in the mITT-VF population achieving SVR₁₂ will be summarized by genotype and overall, along with a two-sided 95% confidence interval using the normal approximation to the binomial distribution and a two-sided 95% confidence interval using the Wilson's score method. Listings of subjects excluded from mITT-VF population will be provided, as applicable.

10.5.1 Imputation Approaches

No imputation methods will be employed other than those described in Section 6.3.

10.6 Efficacy Subgroup Analysis

The percentage of subjects with SVR₁₂ in the ITT population will be calculated with the corresponding two sided 95% Wilson score intervals, for the following subgroups:

- HCV genotype and available subtype (based on final HCV genotype and subtype determination);
- Age (< 65 or ≥ 65 years) and (< 75 or ≥ 75 years);
- Sex (male or female);
- Race (White, Black/African-American, Asian, or other) and black race (black or non-black);
- Baseline BMI (< 30, or ≥ 30 kg/m²);
- Baseline HCV RNA level (< 1,000,000 ≥ 1,000,000 to < 2,000,000; or ≥ 2,000,000 IU/mL);
- Baseline fibrosis stage (equivalent to Metavir F2, F3, or F4);
- Cirrhosis Status (yes/no)
- Baseline platelet count (< 90 or ≥ 90 × 10⁹/L);
- Baseline albumin (< 35 or ≥ 35 g/L);
- Baseline creatinine clearance (< 15, ≥ 15 to < 30, ≥ 30 to < 60, ≥ 60 to < 90, or ≥ 90 mL/min);
- Baseline eGFR (< 15, ≥ 15 to < 30, ≥ 30 to < 60, ≥ 60 to < 90, or ≥ 90 mL/min/1.73 m²);
- History of diabetes (yes/no);
- Subject on stable opiate substitution (yes/no);
- Former injection drug user (yes, within last 12 months; yes, more than 12 months ago; or no)

The 2-sided 95% Wilson score confidence interval will be produced if there are at least 10 subjects in the subgroup.

10.7 Additional Efficacy Analyses

The following additional efficacy endpoints will be summarized for the ITT population:

- The percentage of subjects with HCV RNA < LLOQ at each post-baseline visit in the Treatment Period (using data as observed);
- The percentage of subjects with SVR₄;

The percentage of subjects with virologic failure through Post-Treatment Week 12. The number and percentage of subjects meeting each additional efficacy endpoint will be calculated along with a two-sided 95% CI using the Wilson's score method. Imputations for missing data will be performed as described in Section 6.3 for analysis of SVR, virologic failure, and relapse. The first bulleted endpoint above will be presented using data as observed.

A summary of the subjects who completed treatment and relapsed (defined as **Relapse₁₂**) will be prepared displaying the number of subjects relapsing overall and by SVR visit window (within the SVR₄, SVR₁₂ windows or after SVR₁₂ window), including the subject number and the SVR visit window corresponding to the first HCV RNA value of those indicating the occurrence of relapse. A similar summary will be prepared for subjects who prematurely discontinued treatment and relapsed after having HCV RNA < LLOQ at their Final Treatment Visit. A listing of subjects in the ITT population excluded from the relapse denominator (e.g., study drug duration < 52 days for subjects assigned to 8 weeks of treatment, study drug duration < 77 days for subjects assigned to 12 weeks of treatment, or no post treatment HCV RNA) will be provided, as applicable.

A listing of subject numbers and reasons for non-response to SVR₁₂ will be prepared.

The concordance between SVR₄ and SVR₁₂ will be assessed for the overall population (across treatment arms) by the agreement between SVR₄ and SVR₁₂ and the positive predictive value (PPV) and negative predictive value (NPV) of SVR₄ on SVR₁₂. The agreement between SVR₄ and SVR₁₂ is a percentage defined as the number of subjects achieving both SVR₄ and SVR₁₂ and the number of subjects where both SVR₄ and SVR₁₂

are not achieved. The PPV of SVR₄ on SVR₁₂ is the proportion of subjects who achieve SVR₁₂ out of all subjects who achieved SVR₄. The NPV of SVR₄ on SVR₁₂ is the proportion of subjects who do not achieve SVR₁₂ out of all subjects who did not achieve SVR₄.

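### SAP 10.7 computes SVR4/SVR12 concordance from imputed statuses, so the negative predictive value can rest mostly or wholly on subjects with no post-treatment HCV RNA

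*SAP*

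**What the plan says.** SAP 10.7 (Additional Efficacy Analyses) plans three measures of how SVR4 relates to SVR12: "The concordance between SVR₄ and SVR₁₂ will be assessed for the overall population", across both arms. PPV is the share of SVR4 achievers who achieve SVR12. For NPV: "The NPV of SVR₄ on SVR₁₂ is the proportion of subjects who do not achieve SVR₁₂ out of all subjects who did not achieve SVR₄". Agreement adds the subjects who achieve both to those who achieve neither; no denominator is stated.

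The sentences on concordance do not mention missing data, but the section does: "Imputations for missing data will be performed as described in Section 6.3 for analysis of SVR, virologic failure, and relapse". Its only exception concerns on-treatment HCV RNA below LLOQ: "The first bulleted endpoint above will be presented using data as observed". SAP 10.5.1 adds: "No imputation methods will be employed other than those described in Section 6.3".

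SAP 6.3 has two rules that matter here. For a missing window value, "if the nearest HCV RNA value after the SVR window is unquantifiable or undetectable, then it will be used to impute" the missing one. If a gap remains after that and after any local-laboratory value has been used, "Subjects with missing HCV RNA data in the analysis window, after imputations, will be imputed as a failure".

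SAP Table 2 sets the SVR4 window at Study Drug End Days 3 to 56 and the SVR12 window at Days 57 to 126. The protocol synopsis schedules post-treatment visits only at Weeks 4 and 12; Appendix D adds a post-treatment discontinuation visit.

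**The concern.** PPV and NPV are read as the ability of the week-4 result to predict the week-12 result. That reading needs two results. The windows adjoin and only two visits are scheduled, so the value that fills a missing SVR4 is normally the SVR12 sample itself, and the pair then agrees because both statuses come from one measurement. A subject who leaves after the last dose without a further sample is a failure at both times and is scored as a correct negative prediction.

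Few subjects are expected to miss SVR4 in this trial, so the NPV denominator will be very small and a few subjects without data can fill it. What is at stake is a reported NPV of 100% that reflects loss to follow-up and not virology.

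**Working it through.** **Plan's own figure.** The only design figure is the half-width of the 95% interval at 97% SVR12 with n = 100 (Protocol 8.2, SAP 4.3): 1.96 × √(0.97 × 0.03 / 100) = 0.0334, which reproduces the stated 3.3%. No figure is given for concordance.

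**Step 1: Section 6.3 applied to a missing SVR4 value.**

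| Later data | SVR4 | SVR12 | Result |
|---|---|---|---|
| Week 12 < LLOQ | success (filled) | success | concordant |
| Week 12 ≥ LLOQ | failure | failure | concordant |
| None | failure | failure | concordant |
| Only a value after Day 126, < LLOQ | success (filled) | success (filled) | concordant |

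The exceptions are narrow: a local-laboratory value in the SVR4 window, or two samples in Days 57 to 126 with different results.

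The reverse gap behaves differently. Week 4 < LLOQ with nothing later gives success then failure, which is discordant and counts against PPV.

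**Step 2: effect in 100 subjects.** The missing-data counts are assumptions, since the documents give none. Each cell shows agreement; PPV; NPV.

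| Pattern | Section 6.3 rules | Observed pairs only |
|---|---|---|
| A: 97 < LLOQ at both, 3 no post-treatment data | 100/100; 97/97; 3/3 | 97/97; 97/97; 0/0 |
| B: 92 < LLOQ at both, 5 missed week 4 and < LLOQ at week 12, 3 no data | 100/100; 97/97; 3/3 | 92/92; 92/92; 0/0 |
| C: 92 at both, 5 missed week 4, 1 relapse after week 4, 2 no data | 99/100 = 99.0%; 97/98 = 99.0%; 2/2 | 92/93 = 98.9%; 92/93 = 98.9%; 0/0 |
| D: as C, but 1 no data and 1 week 4 < LLOQ with no week 12 | 98/100 = 98.0%; 97/99 = 98.0%; 1/1 | 92/93 = 98.9%; 92/93 = 98.9%; 0/0 |
| E: 97 at both, 3 week 4 < LLOQ with no week 12 | 97/100 = 97.0%; 97/100 = 97.0%; 0/0 | 97/97; 97/97; 0/0 |

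Raising the missed week-4 visits in C from 5 to 10 (87 at both) leaves the Section 6.3 figures unchanged; observed agreement becomes 87/88 = 98.9%.

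If 2 subjects are observed failures at both times and 4 have no data, NPV is 6/6 under the rules and 2/2 in observed pairs. The percentage is the same, but 4/6 = 67% of the denominator carries no post-treatment HCV RNA.

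**Step 3: how thin the NPV denominator may be.** Protocol Section 3.0 reports 23 virologic failures among treatment-naïve and TE-PRS subjects, and Table 2 reports SVR12 in 2206/2256. Assuming the two describe one pool, the rate is 23/2256 = 1.02%, about one per 100, and the chance of none in 100 is (1 − 0.0102)^100 = 0.36. Across assumed rates of 0.5%, 2% and 3% that chance is 0.61, 0.13 and 0.05. Leaving out the one reinfected subject gives 22/2256 = 0.98% and 0.38.

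Of the 2256 − 2206 = 50 non-responders, 50 − 23 = 27 (54%) were not virologic failures.

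**The case against.** The strongest reply is about weight. Concordance serves no stated objective, is not among the additional endpoints in Protocol 8.1.2.5, and involves no hypothesis test. The SVR rates, relapse and on-treatment failure are unaffected. SAP 10.3 and 10.7 already require listings of SVR12 non-responders by reason, with missing follow-up as its own category, and a listing of subjects excluded from the relapse denominator. A careful reader could work out which negatives have no data. All of this stands. The listings do not correct the NPV, but they limit the harm.

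It can also be said that the documents never state that the analysis is about observed week-4 values. Agreement between the two endpoints as defined is a coherent description, so preferring observed pairs is partly a matter of judgement. That stands too, and is a reason to allow both versions.

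Backward filling needs a gap across the whole of Days 3 to 56, and HCV RNA is drawn at the post-treatment discontinuation visit, so some early leavers will have a value.

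A reader might infer that the rules always inflate agreement. They do not: patterns D and E lower it. A reader might also infer that the 27 earlier non-responders who were not virologic failures were mainly missing data. The protocol gives no such breakdown, and under SAP 10.1 a subject who stops treatment early and has quantifiable HCV RNA afterwards can fall outside virologic failure while still having an observed result.

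Finally, restricting the analysis strictly to observed pairs would do damage of its own. SAP 6.3 discards HCV RNA values from the start of any new HCV treatment, so an early relapser who is retreated before the SVR12 window would be dropped, although that subject is a true negative.

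**Conclusion.** The point holds, mainly for NPV, and is minor. Subjects with no SVR4 value are almost always concordant under Section 6.3, and those with no post-treatment HCV RNA enter both the numerator and the denominator of NPV, which can then read 100% where observed data give no estimate. In the patterns examined, agreement and PPV shift by at most 3 percentage points, in either direction.

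This rests on reading the imputation sentence in SAP 10.7 as covering concordance, which the single as-observed exception and SAP 10.5.1 support, and on assumed missing-data counts. It would be tempting to carry the criticism over to the efficacy result. The documents do not support that: the primary endpoint is the SVR12 rate, in which counting missing values as failures is a separate, stated choice that this point leaves alone.

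**What to change.** In SAP 10.7:

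- Compute agreement, PPV and NPV in subjects with an observed HCV RNA value, from the central or a local laboratory, in both the SVR4 and SVR12 windows, without backward imputation and without counting missing values as failures.
- Keep as SVR12 failures those subjects with an observed virologic failure whose later values are excluded because they started new HCV treatment.
- Use the resulting count as the agreement denominator, and report how many subjects are excluded and why.
- The imputed version may stay alongside, with the number of imputed subjects shown in each cell.

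Leave Section 6.3 unchanged for the SVR4 and SVR12 rates. SAP 10.1 already limits relapse analyses to subjects with at least one post-treatment value, so a restriction of this kind is not new to the plan.

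The cost is a sentence or two in the SAP and a small programming change. The price is a smaller denominator, and NPV may have to be reported as not estimable.
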